4.2 Exclusion Criteria

- 1. Not willing or able to sign consent.
- 2. Patients who have used topical or systemic corticosteroid therapy for any reason in the previous 6 weeks.
- 3. Patients who have been treated with acid-suppressing medications (PPI or H2 receptor antagonists) in the previous 6 weeks.
- 4. Patients on immunosuppressive or immunomodulating medications in the previous 6 weeks.
- 5. Patients with known allergies or hypersensitivity to anti-histamines.
- 6. Patients who have contraindications to the procurement of biopsies including patients who have known bleeding disorders, a history of bleeding diathesis, or who are currently using warfarin or clopidogrel.
- 7. Patients who have a contraindication to the performance of an esophagogastroduodenoscopy (EGD) including previous cardiopulmonary arrest during an endoscopic procedure.
- 8. Patients who are pregnant.

4.3 Subject Recruitment, Enrollment and Screening

After institutional review board approval, all patients who present to the Mayo Clinic Florida Esophageal Diseases Clinic or General Gastroenterology Clinic with the diagnosis of EoE who meet enrollment criteria will be offered enrollment into the study. All enrolled patients will be entered by the physician through written informed consent.

The appointment schedule for the Esophageal Diseases clinic and the General Gastroenterology clinic at the Mayo Clinic Florida will be reviewed 1-5 days in advance by the study coordinator to determine which patients are coming for dysphagia or EoE. If the indication for the appointment is dysphagia, the study coordinator will review the patient's chart or outside records to determine if there is evidence of EoE. The physician that is scheduled to see any patient that is identified as having EoE will be contacted prior to the patients' appointment and asked if he or she agrees to have the patient approached for study enrollment.

We will also make general announcements to our Gastroenterology Division about the study in an attempt to recruit patients with EoE at our center.

Once patients are identified, they will be approached by our study coordinator and informed of the study. They will be provided with a consent form. The consent form will be documented by their signature on the consent form and this will be entered into the patient's permanent medical record.

Consent will either be performed in person face-to-face on the Mayo Clinic Florida Campus in a private meeting room, or via Zoom meeting, in the setting of the coronavirus pandemic. This will be per the patient preference. If consent is performed via Zoom meeting, the study coordinator or investigator will teleconference from a private exam or conference room on the Mayo Clinic Florida campus, and the study participant will teleconference from a private

location of their choosing. To confirm the study participant's identity by Zoom, the coordinator or investigator will ask them to confirm their name and date of birth. All included study participants must be willing and able to sign consent and be age 18 or older. The study will not include adults lacking capacity. The link for the Zoom meeting and consent will be emailed to the patient at an email of their choice, in the week prior to the Zoom meeting. If study participants request a hard copy of the consent, this will be mailed at the request of the study participant.

Women of child-bearing age (18-50) and potential will be given a urine pregnancy test prior to enrollment in the trial.

In the Mayo Clinic Florida Esophageal Diseases Clinic, we see approximately 3-5 patients with EoE per week. This amounts to an estimated 150 patients per year. Assuming we can enroll at least half of these patients in our study, the study will take approximately 12 to months complete.

4.4 Early Withdrawal of Subjects

4.4.1 When and How to Withdraw Subjects

Subjects may be withdrawn from the study for safety issues, failure of subject to adhere to protocol requirements, and subject decision to withdraw from the study. Safety issues include adverse effects from the study drugs, or inability to tolerate the study drugs. Failure of subjects to adhere to protocol requirements includes adherence to the medication regimen, absence of follow-up visits, or not completing study questionnaires. As there is a 6 week wash out period prior to study inclusion, patients may have worsening of symptoms of EoE while off prior medications. Patients who have worsening or relapse of symptoms of EoE while enrolled in the trial will be removed from the study.

For patients who do not tolerate the study drug, other treatment alternatives will be offered, including PPIs, corticosteroids, and/or diet modification.

Data will be collected on withdrawn subjects up until the point of study withdrawal. A scheduled follow-up appointment will be ordered in clinic following study withdrawal.

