4.4.2 Data Collection and Follow-up for Withdrawn Subjects

A follow-up appointment will be ordered at the 12 week period after initiation of the study drug or placebo.

5 Study Drug

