6.2 Visit 2 (4 week follow-up after starting study drugs)

This visit will occur per participant preference, either via phone call or in person by appointment, with the study coordinator and will occur at 4 weeks plus or minus a one week period after initiation of the study drugs. Study participants will review medication compliance and adverse effects.

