6.4 Visit 4 (12 week follow-up)

At the 12 week follow-up visit with a physician, we will review the results of the DSQ to be completed for weeks 10-12 of the study drugs. The 12 week follow-up appointment will occur no earlier than 12 weeks after initiation of the study drug and no later than 14 weeks after initiation. The patient will meet with one of the study investigators, and be consented for an EGD. An EGD with esophageal biopsies will be performed. Prior to EGD, a complete blood count and basic

metabolic panel will be ordered as routine per institutional policy. Either KD or DF will perform the EGD in the endoscopy suite, per our institution's standard protocol. Any macroscopic abnormalities seen in the esophagus will be documented and photographed. Any lesions in the upper digestive tract seen on EGD will be biopsied and treated as deemed appropriate by the performing endoscopist. Biopsy specimens will be labeled and placed in a container and labeled with the patient's ID number.

The eosinophil count will be determined by the study pathologist for the post-treatment exam using a previously validated protocol. [2, 3] Four esophageal biopsies will be sampled from both the distal esophagus (3cm above the GE junction) and proximal esophagus (at least 10 cm above the GE junction) to maximize sensitivity of detecting eosinophils.[1] On each biopsy fragment, 5 high-power fields will be examined and the overall peak eosinophil count determined from the field deemed to be most inflamed from all esophageal levels and all high power fields. [4]

Symptomatic improvement will be defined as at least 2 levels on the dysphagia questionnaire.

Study Activity	Week 0 (initial enrollment appointment)	Week 6	Week 10	Weeks 14-16 (follow-up appointment)
Study Agent(s) (weeks 2-14)		X	X	
Informed consent	X			
Physician office visit with medication review and physical exam	X			X
Phone or office visit with study coordinator		X	X	
Pill count		X	X	X
Drug diary		X	X	
Adverse event evaluation		X	X	Х

B-HCG (non-menopausal females)	X		
Dysphagia Symptom Questionnaire (complete weeks 0-2 and 12-14)	X		X
CBC and BMP			X
EGD w/ biopsy			X

7 Statistical Plan

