7.2 Statistical Methods

Descriptive Statistics

Means and standard deviations will be used to summarize quantitative and continuous variables. These will include age, dysphagia questionnaire scores, and eosinophils per hpf on histology. Frequencies and percentages will be used to summarize categorical variables including gender; the proportion of patients that have symptomatic and histologic improvement in symptoms on placebo; and the proportion of patients that have symptomatic and histologic improvement in symptoms on anti-histamines.

Handling of Missing Data

We will perform data queries for missing dysphagia questionnaires and pathology reports.

Primary Hypothesis: Antihistamines are effective for the treatment of EoE and will result in symptomatic improvement as assessed by patient questionnaires and endoscopic and histologic improvement as assessed by endoscopic score and by eosinophil counts on biopsy.

Continuous demographic variables, peak eosinophil counts and dysphagia and GERD questionnaire scores at baseline and 12 weeks will be compared between the treatment and placebo arms using a two-sample t test or Wilcoxon rank sum test where appropriate. Categorical demographic variable and percentage of patients with histologic response of ≤15 eos/hpf at 12 weeks will be compared between the two arms using Chi-squared test or Fisher's exact test. The changes in peak counts and questionnaire scores in the treatment arm from baseline to 12 weeks will be compared suing a paired t-test or signed rank test

All tests will be two-sided with alpha level set at 0.05 for statistical significance.

Interim Analysis

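### Section 4.4.1 lets a missed questionnaire or interim contact end study participation, which can cost the Visit 4 biopsy that supplies the primary efficacy value

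*Combined protocol and SAP*

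**What the plan says.** Section 4.4.1 makes withdrawal discretionary: "Subjects may be withdrawn from the study for safety issues, failure of subject to adhere to protocol requirements, and subject decision to withdraw". It then says what non-adherence covers: "Failure of subjects to adhere to protocol requirements includes adherence to the medication regimen, absence of follow-up visits, or not completing study questionnaires". No number of missed entries or visits is given. On data, the same section says "Data will be collected on withdrawn subjects up until the point of study withdrawal". Section 4.4.2 adds, for withdrawn subjects, "A follow-up appointment will be ordered at the 12 week period after initiation of the study drug or placebo". It does not mention endoscopy, biopsy or use of that visit's data.

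The primary efficacy endpoint (3.4) is the maximum eosinophil count after 12 weeks. Its post-treatment value comes only from the Visit 4 endoscopy (6.4). The DSQ is a secondary endpoint (3.5). It is filled in daily for two weeks before treatment and again at the end of treatment; at Visit 4 "we will review the results of the DSQ to be completed for weeks 10-12 of the study drugs". Visits 2 and 3 are both titled as follow-up visits, so the visit ground reaches them. Their stated content is the same: "Study participants will review medication compliance and adverse effects".

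On missing data, section 7.2 says only: "We will perform data queries for missing dysphagia questionnaires and pathology reports".

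**The concern.** The ground for withdrawal and the measurement lost are not the same thing. An unfilled diary day weakens the DSQ, and a missed week-4 or week-8 contact weakens the interim safety record. Neither prevents a valid biopsy at week 12. Yet withdrawal is from the study, not only from study drug, and nothing in 4.4.1 or 4.4.2 preserves the biopsy.

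Two things are at stake. One is precision: the trial plans 20 evaluable patients per arm, and its 20% dropout allowance has to cover every cause of loss. The other is selection. Patients who stop filling in a symptom diary or miss a call may be doing well, doing badly or having side effects, so they are unlikely to be a random subset. The choice to withdraw them has no threshold, and the documents do not say who makes it. Sections 5.7 and 8.4 leave the PI and one co-investigator unblinded, and 4.4.1 does not keep them out of the decision. A reader of the results could not rule out that knowledge of allocation affected who reached the biopsy.

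**Working it through.** **1. Tracing a patient through the text.**
- A patient has gaps in the DSQ, or misses the week-4 or week-8 contact. Under 4.4.1 this counts as non-adherence, whatever its extent.
- The study team may withdraw the patient from the study (4.4.1).
- Data collection stops at that point (4.4.1).
- A 12-week appointment is ordered (4.4.2), with no endoscopy or biopsy named.
- The only post-treatment eosinophil count comes from the Visit 4 endoscopy (6.4). If it is not done, the primary efficacy value is missing.
- Section 7.3 defines an all-randomized population. With no biopsy, and no missing-data rule in 7.2 beyond queries, that population cannot include this patient for the primary efficacy endpoint.

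By contrast, section 5.4 does set a threshold (70%) for drug compliance.

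**2. The plan's own sample size figures.** Inputs from 7.1 and 7.2: SD of change 50 eos/hpf, two-sided alpha 0.05, power 80%. Baseline 100 eos/hpf is an assumption within the stated 80–110.

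n per arm = 2 × (1.960 + 0.842)² × SD² / δ²
- 40% difference, δ = 40: 2 × 7.85 × 2500 / 1600 = 24.5, so 25. Reproduced.
- 50% difference, δ = 50: 2 × 7.85 × 2500 / 2500 = 15.7, so 16. Reproduced.
- Enrolment: 40 / (1 − 0.20) = 50. Reproduced.

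Over the stated baseline range, n per arm runs from 39 (baseline 80) to 21 (baseline 110) for a 40% difference, and from 25 to 13 for a 50% difference.

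**3. What lost biopsies cost.** Power ≈ Φ(δ / (SD × √(2/n)) − 1.960), baseline 100, SD 50:

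| Biopsies per arm | 40% difference | 50% difference |
|---|---|---|
| 25 | 80.7% | 94.2% |
| 20 | 71.6% | 88.5% |
| 18 | 67.0% | 85.1% |
| 16 | 61.9% | 80.7% |

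Starting from 20 per arm, each further two biopsies lost per arm cost about 5 points for a 40% difference (71.6 − 67.0 = 4.6; 67.0 − 61.9 = 5.1) and about 4 points for a 50% difference (88.5 − 85.1 = 3.4; 85.1 − 80.7 = 4.4).

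**4. How many patients the DSQ ground could reach.** The documents give no rate of missed entries. Assume that each daily entry is missed independently with probability p and that one gap is enough. Over the 14 final entries, the share with at least one gap is 1 − (1 − p)^14:
- p = 1%: 1 − 0.869 = 13%
- p = 2%: 1 − 0.754 = 25%
- p = 5%: 1 − 0.488 = 51%

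This is the share for whom the ground would be available on a literal reading. It is not a forecast of withdrawals, which the documents do not allow anyone to compute.

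**The case against.** **The ground is discretionary.** Section 4.4.1 uses permissive wording here and mandatory wording for relapse of symptoms; 5.4 is also mandatory for poor compliance. Nothing says that one missed diary day triggers withdrawal. This stands, and it is why the point is about what the rule allows. It does not remove the concern, because discretion without a threshold, in a partly unblinded team, is itself a route to selection.

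**Sections 4.4.1 and 7.2 contradict each other.** A reader might infer this, since one allows withdrawal and the other a query for the same gap. The documents do not support it. A query is a data-cleaning step and can come before any decision on participation; 7.2 does not say that the patient is kept in. What remains is that no order between the two is given.

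**A missed interim contact touches nothing primary.** A reader might infer this too, and it would be wrong. Safety and tolerability is a primary endpoint (3.4), and 3.6 makes the monthly phone visits part of the safety assessment. Such a gap does damage primary safety data. It does not damage the eosinophil count, and withdrawing the patient recovers no safety data.

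**The DSQ route is narrow.** The final DSQ is reviewed at Visit 4, the visit that leads to the endoscopy, and no earlier check of those entries is described. To lose the biopsy this way, the physician would have to find the gap and then not proceed. That makes the route less likely. The text does not exclude it, and it leaves the pre-treatment diary and the two interim contacts as earlier routes.

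**Withdrawn subjects are still seen at 12 weeks.** True under 4.4.2, but with no biopsy named and data collection already ended, that appointment does not secure the primary value.

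**Conclusion.** The point holds as a weakness in the withdrawal rule. As written, a gap in a secondary diary or a missed week-4 or week-8 contact can lead, at the team's discretion and with no threshold, to loss of the only post-treatment primary efficacy measurement. The trial has little slack: at baseline 100 and SD 50, power for a 40% difference is 71.6% with 20 biopsies per arm and 61.9% with 16.

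The size of the loss from this rule alone is unknown. A reader might take the miss-rate arithmetic further, count all 28 daily entries (25% to 76% with a gap at 1% to 5% per day) and set that against the 20% dropout allowance. The documents do not support that comparison. The rates and their independence are assumed, half of those entries precede study drug, and being open to a discretionary ground is not the same as dropping out. The direction of any selection bias is also unknown. The sample size arithmetic is not at fault. This is worth correcting because the loss is avoidable and the correction is cheap; it does not by itself invalidate the design.

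**What to change.** Amend 4.4.1 and 4.4.2, on study participation and data only:
- Remove incomplete questionnaires from the grounds for withdrawal from the study.
- Narrow the missed-visit ground so that a missed week-4 or week-8 contact does not by itself end study participation. Leave absence from Visit 4 as it is.
- State that these patients, if willing, still have the already planned Visit 4 endoscopy with biopsies and are included in the primary analysis.
- State that the missing item is queried under 7.2 and affects only the endpoint to which it belongs.
- State that safety decisions and attempts to re-contact the patient are unchanged.

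Nothing is lost for sensitivity analysis, since 7.3 already defines protocol-compliant and all-completed populations.

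The cost is an amendment to wording, with no new procedure or visit and no change to any sample size figure. The downside is that some patients will have a biopsy but no usable final DSQ, or an incomplete interim safety record.

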5.4 Subject Compliance Monitoring

In a diary, patients will record time of medication administration before breakfast and evening meal. At the follow-up visit following the 12 week intervention period, a pill count will be performed. Patients who are not more than 70% compliant will be withdrawn from the study.

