5.8.3 Dispensing of Study Drug

On the 12 week follow-up appointment, the treating physician will perform a pill count to document the amount of drug remaining. The pill count will be entered into the study database.

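### Removal for worsening symptoms or low compliance, with no stated week-12 data or analysis set for those removed, leaves the between-arm comparison selected after randomization

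*Combined protocol and SAP*

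**What the plan says.** All references are to the combined protocol and SAP.

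- **Worsening (4.4.1).** "Patients who have worsening or relapse of symptoms of EoE while enrolled in the trial will be removed from the study". No threshold or definition of worsening is given. On data: "Data will be collected on withdrawn subjects up until the point of study withdrawal".
- **Follow-up of withdrawn patients (4.4.2).** "A follow-up appointment will be ordered at the 12 week period after initiation of the study drug or placebo". No EGD, biopsy or DSQ is named.
- **Visit 4 (6.4).** The DSQ and biopsy belong to this visit: "At the 12 week follow-up visit with a physician, we will review the results of the DSQ to be completed for weeks 10-12", and "The patient will meet with one of the study investigators, and be consented for an EGD".
- **Compliance (5.4).** "At the follow-up visit following the 12 week intervention period, a pill count will be performed". Then: "Patients who are not more than 70% compliant will be withdrawn from the study". Section 5.8.3 agrees on timing, but the schedule in 6.4 also marks pill counts at weeks 6 and 10, and 4.4.1 lists poor adherence as a ground for withdrawal with no time attached.
- **Analysis (7.2, 7.3).** Missing questionnaires and pathology reports are to be queried; nothing else is planned for missing data. Four populations are defined, from all-randomized to all-completed. None is assigned to an endpoint, and the between-arm tests name no population.
- **Blinding (5.7, 8.4).** The PI and one co-investigator know the allocation.

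**The concern.** Both rules act after randomization and depend on things that treatment can change. Worsening symptoms are close to the DSQ endpoint itself and plausibly related to the eosinophil count. Adherence may depend on tolerability or perceived benefit. If such patients contribute no week-12 data, or contribute data that are then set aside, the patients compared at week 12 are no longer the groups that were randomized. The 20% dropout allowance in 7.1 replaces numbers; it does not address who is lost. A data query cannot recover a biopsy that was never taken.

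Because no population is assigned, the choice between all-randomized and all-completed can also be made after the results are known.

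The clinical reason for taking a worsening patient off study drug is sound. What is at issue is which data are collected and analysed afterwards.

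**Working it through.** **1. The plan's own figures.** From 7.1: SD of change 50 eos/hpf, two-sided alpha 0.05, 80% power. The 40% and 50% differences are read as 40 and 50 eos/hpf, which assumes a baseline of 100, inside the stated 80-110.

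n per arm = 2 × [(1.960 + 0.842) × 50 / difference]²

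- Difference 40: 24.5, so 25.
- Difference 50: 15.7, so 16.
- Enrolment: 40 / 0.80 = 50.

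All three reproduce.

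**2. Worsening rule, same threshold in both arms.** Assumptions that the documents do not give: the worsening score and week-12 count are jointly normal with correlation ρ; the true count difference is -40; the drug shifts the worsening score by -0.8ρ SD (that is, ρ × 40/50); and patients above one common threshold are removed. For an arm with removed share d:

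shift in mean count of those remaining = -ρ × 50 × φ(z) / (1 - d), where z is the standard normal quantile at 1 - d

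With ρ = 0.5:

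| Placebo removed | Active removed | Placebo shift | Active shift | Difference in those remaining |
|---|---|---|---|---|
| 20% | 10.7% | -8.75 | -5.17 | -40 - 5.17 + 8.75 = -36.4 |
| 30% | 17.8% | -12.42 | -7.91 | -40 - 7.91 + 12.42 = -35.5 |
| 40% | 25.7% | -16.10 | -10.84 | -40 - 10.84 + 16.10 = -34.7 |

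Overall removal in the first two rows is about 15% and 24%, so the plan's 20% dropout lies between them. Over ρ = 0.3 to 0.7 and these removal rates, the difference runs from -38.6 to -30.1. With no effect on counts or symptoms and 30% removed, simulated two-sided rejection among those remaining was 5.4%, split evenly. Under this model the bias is against the drug.

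**3. Worsening rule, removal differing by arm.** Assume no effect on counts, 25 randomized per arm, and 30% of active against 10% of placebo removed for worsening. The ratios φ(z)/(1 - d) are 0.497 and 0.195.

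- Spurious difference in favour of the drug: ρ × 50 × (0.497 - 0.195) = 4.5 at ρ = 0.3 and 7.5 at ρ = 0.5.
- Standard error: 50 × √(1/17.5 + 1/22.5) = 15.9.
- False pro-drug results: Φ(-1.96 + 4.53/15.94) = 4.7% and Φ(-1.96 + 7.54/15.94) = 6.9%, against a nominal 2.5%.

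Reversing the split gives the same bias against the drug. The documents neither predict nor exclude such an imbalance.

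**4. DSQ.** Here selection is direct. Assume a 0.4 SD symptom effect and 30% of placebo removed under a common threshold. The ratios are 0.497 (placebo) and 0.316 (active). If the worsening score correlates r with DSQ, the difference remaining is 0.4 - r × (0.497 - 0.316), which is 0.29 SD at r = 0.6 and 0.22 SD at r = 1.0. That is a loss of 27% to 45%.

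**5. Compliance rule.** Two-sample t-test power for a difference of 40 and SD 50 is 79% with 25 per arm, 69% with 20, 64.5% with 18 and 59% with 16. Below 20 per arm, setting aside two biopsied patients per arm costs about 5 points. This is loss of power only. The number affected, and any bias from excluding them, cannot be derived.

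**The case against.** The strongest reply is that the 12-week appointment in 4.4.2 is Visit 4. It stands under a heading on data collection, and 3.6 places the EGD with biopsies at the 12-week follow-up. On that reading the biopsy is already intended, and an all-randomized population is available in 7.3. This is a fair reading, and for that reason it would be wrong to infer that withdrawn patients certainly go without a biopsy. But 4.4.1 ends data collection at withdrawal, 4.4.2 names no procedure, and a population that is defined but not assigned decides nothing.

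A reader might infer that the rules necessarily favour the drug, or that they can never do so. Neither follows. With a common threshold the bias in peak count is against the drug. With removal that differs by arm it can go either way, and undefined worsening together with an unblinded PI and co-investigator makes that possible, though not predicted.

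A reader might also infer that every poorly compliant patient has a biopsy that is then discarded. That is the usual case, because the deciding count falls at the visit where the biopsy is due, but 4.4.1 and the earlier pill counts allow withdrawal before it.

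It can also be said that removals during washout or the two-week DSQ run-in come before any dose. That stands: they cannot bias the comparison through a treatment effect.

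**Conclusion.** The concern holds and should be fixed. The textual facts are firm: mandatory removal for worsening, data to withdrawal only, withdrawal at 70% compliance or less, no stated Visit 4 procedures for withdrawn patients, and no assigned population.

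The size is unknown. For peak count under one common threshold it is modest and conservative, roughly a tenth of an assumed 40 eos/hpf effect at correlation 0.5 (3.6 to 5.3 eos/hpf). That label does not extend to DSQ, where the proportionate loss could be larger, nor to removal that differs by arm, where false pro-drug results could rise. Every removal rate and correlation used is an assumption.

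**What to change.** 1. **Section 5.4.** Delete the withdrawal at 70% or less. Analyse those patients' Visit 4 data and use the cut-off only to define the protocol-compliant population.
2. **Sections 4.4.1 and 4.4.2.** Separate stopping study drug from leaving the study, and leave clinical care unchanged. State that the 12-week appointment is Visit 4, with its planned EGD, biopsy and DSQ, where the patient consents and it is clinically acceptable. Record any rescue therapy and its date.
3. **Sections 7.2 and 7.3.** Make the all-randomized population primary for between-arm comparisons. For histologic response, count removal for worsening, rescue therapy or no week-12 biopsy as non-response. For peak count, analyse all available Visit 4 biopsies regardless of adherence or drug discontinuation, call this an observed-case analysis with some selection remaining, and show sensitivity analyses for post-rescue and missing biopsies. Report removals by arm, by reason, and before or after the first dose.

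**Cost.** Protocol and SAP text, using the EGD already planned for each patient. Under the narrow reading of 4.4.1, some withdrawn patients would have a sedated EGD, with the risks in 3.6, that they would otherwise not have had; 6.4 takes consent for it, so they can decline. Some biopsies will follow stopped drug or rescue, so the effect may be diluted.

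A power gain is not assured. In simulations with 25 per arm, correlation 0.5 and 30% of placebo removed, Wilcoxon power was 58% in those remaining. It rose to 69% if half of the removed patients were biopsied without rescue, but only to 59% if the drug effect was lost after stopping. The case for the change is a comparison fixed in advance and closer to the randomized groups.
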